Surprisingly, mild psoriasis was characterized by significantly higher IL-17A expression, stronger expression of the core psoriasis transcriptome, and by higher numbers of T-cells in skin lesions. In contrast, severe psoriasis was characterized by stronger expression of some epidermal response genes (TGFA, CALM1, SMPD3 & IL1RL2). However, a key molecular distinction between mild and severe psoriasis was higher expression of negative immune regulatory genes (CTLA4, PD-L1 & CD69) in mild lesions compared to severe psoriasis lesions.

These data have relevant implications for therapy of psoriasis—first they suggest that anti-IL-17A approaches used in severe psoriasis might be equally (or even more) effective in mild psoriasis. Secondly, restoration of immune tolerance might be more easily achieved in mild psoriasis due to higher “regulatory” immune tone that effectively prevents unbounded T-cell expansion. Thus, short-term anti-IL-17A treatment of mild psoriasis might prevent the recurrence and eventually cure psoriasis. The aim of the study is to test this hypothesis by exploring whether 3 months or 6 months of Secukinumab treatment will prevent relapses after medication has been discontinued in mild psoriasis patients.

12.4 * Engaging Stakeholders: Describe any plans to engage other stakeholders (Scientists, practitioners, patients, advocacy groups, etc.) for hypothesis generation, or feasibility purposes.

We will engage stakeholders, including participants, their families, their health care providers, and the study sponsor, and to assure safe progression of the study and to address any concerns may arise.

12.5 * Hypothesis

Describe the *research hypothesis* in a single sentence.

COSENTYX (secukinumab) is efficacious in treating mild, chronic plaque type of psoriasis in adults.

12.6 * Aim(s)

Indicate how you will *address the hypothesis* (e.g., to compare groups, to estimate a parameter, to ascertain feasibility). Since the sample size determination is usually based on the primary aim only, the primary aim should be sufficient to justify the study.

- 1) To evaluate the efficacy of secukinumab for the complete resolution of mild plaque-type psoriasis after 3 months of secukinumab treatment by comparing the secukinumab-receiving mild psoriasis subjects (Group 1) and the placebo-receiving mild psoriasis subjects (Group 2).

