- Assessment of psoriasis, PGA, PASI with BSA, PASE, DLQI
- Adverse event assessment

Translational research: 6-mm punch skin biopsies from lesional and non-lesional skin and blood samples will be obtained at baseline and weeks 12, 24, 72, at the time of psoriasis relapses, and at early termination. Genomic profiling of psoriasis skin will be conducted with the Affymetrix Human Genome U133 Plus 2.0 Array and RT-PCR. The phenotypes of activated T cells and regulatory T cells in psoriasis patients' blood will be studied by flow cytometry. Inflammatory and cardiovascular proteins in the blood will be investigated to develop a biomarker with Proximity Extension Assay technology (OLINK®).

Structure: Double Blind, Two-arm parallel group design, Randomized 1:1.

12.10 * Data Analysis

Describe method(s) of data analysis.

For the comparison between proportions a Fisher exact test will be performed in any case. The results will be presented as contingency tables and odd ratios will be calculated. 95% Confidence Intervals will be provided. To achieve the primary objective

The comparison between times of relapse must be done using a Wilcoxon-Mann-Whitney test. A Kaplan Meier analysis will be used to establish the relapse survival curve for each group and

the log-rank test will be made. A step-down hierarchical closed testing procedure will be done considering the order: PASI75, PASI90, IGA0.

12.11 * Explain the rationale for the choice of statistical measures and the number of participants proposed for the study, including the power calculations when applicable.

1. Sample Size Calculation for Primary Objective/First outcome (3 co-primary endpoints are subject to a step-down hierarchical closed testing procedure)

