Langley et al. (2014) presented the results of two Phase 3 trials for Secukinumab: ERASURE and FIXTURE. Among others outcomes Langley reported the proportion of subjects with moderate or severe Psoriasis who achieve PASI75 (PASI score improvement over 75%) after 12 weeks of treatment in the 2 cohorts treated with Secukinumab 300 mg and the 2 Placebo cohorts with 245, 323, 246 and 324 subjects respectively. The worst scenario observed on Langley's results is: largest Placebo proportion=0.05 and smallest Secukinumab proportion=0.77. Assuming Langley's results as preliminary data, to find significant differences between groups by using a one-tail Fisher exact test with power equal to 0.95 and 99.9% of significance level, a sample size of 19 patients at each group (N=38) will be required. Considering the 5.6 % of dropout reported by Langley will be necessary to recruit 20 patients for each group (N=40). Power analysis for 3 co-primary endpoints and 19:19 patients is reported in the following table:

ENDPOINT	TREATMENT OBSERVED PROPORTION *	PLACEBO OBSERVED PROPORTION *	OBSERVED EFFECT SIZE*	SIGNIFICANCE LEVEL	POWER	DETECTABLE EFFECT SIZE
PASI 75	0.77	0.05	0.72	0.05	0.8	0.49
				0.05	0.9	0.55
				0.05	0.95	0.60
				0.01	0.8	0.42
				0.01	0.9	0.48
PASI 90	0.54	0.02	0.52	0.05	0.8	0.4
				0.05	0.9	0.47
				0.05	0.95	0.52
				0.01	0.8	0.52
				0.01	0.9	0.59
IGA0	0.24	0.01	0.23	0.05	0.8	0.37
				0.05	0.9	0.44
				0.05	0.95	0.50
				0.01	0.8	0.50
				0.01	0.9	0.56
				0.01	0.95	0.61

OR

ENDPOINT	TREATMENT OBSERVED PROPORTION *	PLACEBO OBSERVED PROPORTION *	OBSERVED EFFECT SIZE*	SIGNIFICANCE LEVEL	ESTIMATED POWER TO DETECT OBSERVED EFFECT SIZE
PASI 75	0.77	0.05	0.72	0.05	0.99
				0.01	0.99

PASI 90	0.54	0.02	0.52	0.05	0.99
				0.01	0.94
IGA 0	0.24	0.1	0.14	0.05	0.46
				0.01	0.25

* Langley et al. (2014)

2. Power Analysis for Exploratory Objectives/First outcome

Assuming the proportion of 300 mg secukinumab patients who achieve PASI 100 at week 24 as reported by Langley (0.4), the allocation ratio of subjects who achieve PASI 100 and subjects who not achieve PASI 100 for Group 1 (6 month of Secukinumab) will be 8:11. On that case a Fisher exact test to compare the proportion of patients who experience relapse with power equal to 0.80 and 95% of significance level will be able to detect significant differences only if the following relationship between proportions is observed:

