Proportion of patients from Group 1, who achieve PASI 100 at week 24 and experience relapse	Proportion of patients from Group 1, who not achieve PASI 100 at week 24 and experience relapse
0.00	0.45
0.13	0.73
0.25	0.82
0.38	0.91
0.50	1.00

Assuming the proportion of 300 mg secukinumab patients who achieve PASI 100 at week 12 as reported by Langley (0.3), the allocation ratio of subjects who achieve PASI 100 and subjects who not achieve PASI 100 for Group 1 (6 month of Secukinumab) will be 6:13. On that case a Fisher exact test to compare the proportion of patients who experience relapse with power equal to 0.80 and 95% of significance level will be able to detect significant differences only if the following relationship between proportions is observed:

Proportion of patients from Group 2, who achieve PASI 100 at week 24 and experience relapse	Proportion of patients from Group 2, who not achieve PASI 100 at week 24 and experience relapse
0.00	0.54
0.17	0.77
0.33	0.85
0.50	1.00

With the previous assumptions, the allocation ratio of subjects who achieve PASI 100 in Groups 1 and 2 will be 8:6. On that case a Fisher exact test to compare the proportion of patients who experience relapse with power equal to 0.80 and 95% of significance level will be able to detect significant differences only if the following relationship between proportions is observed:

Proportion of patients from Group 1 who achieve PASI 100 at week 24 and experience relapse	Proportion of patients from Group 2 who achieve PASI 100 at week 24 and experience relapse
0.00	0.67
0.13	0.83
0.25	1.00

3. Power Analysis for Exploratory Objective/Second outcome

To compare the time to relapse between groups with a sample size of 19:19 a Wilcoxon-Mann-Whitney test for nonrelated samples with power equal to 0.8 and 95% of significance level will be able to detect differences only if the effect size observed is equal or larger than 0.96

12.12 * Will samples be coded?

Yes No

If Yes, Please describe coding scheme consistent with GCP. If samples will not be coded, please provide justification for this proposed departure from GCP practice.

Samples will be coded using GCP with the following sequence

NSK__-001. NSK__-002, etc.

If available, upload the Data and Sample Sharing Management Plan approved by RU IT.

Version	Title	Category	Expiration Date	Document Outcome	Checked Out	View Document
No Document(s) have been attached to this form.						

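### Fisher's exact test is valid but conservative at these sample sizes; Boschloo's exact test never loses power, though its gain depends on a sidedness and alpha that section 12.10 leaves open

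*Combined protocol and SAP*

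**What the plan says.** Section 12.10 (Data Analysis) sets one method for binary outcomes: "a Fisher exact test will be performed in any case". It adds contingency tables, odds ratios and 95% confidence intervals, and the fixed testing order PASI 75, PASI 90, IGA 0. It gives neither the sidedness nor the significance level of the analysis.

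Section 12.11 sizes the trial on PASI 75 with a "one-tail Fisher exact test with power equal to 0.95 and 99.9% of significance level", concluding that "a sample size of 19 patients at each group (N=38) will be required"; with dropout allowed for, 20 per arm are recruited. Its second power table gives IGA 0 power of 0.46 at 0.05 and 0.25 at 0.01.

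For the relapse comparisons, section 12.11 works with subsets of 8:11 and 6:13 (PASI 100 achievers against non-achievers). Between the groups, it says that "the allocation ratio of subjects who achieve PASI 100 in Groups 1 and 2 will be 8:6". Fisher's test is used throughout. An unconditional exact test is not mentioned.

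**The concern.** Fisher's test conditions on the total number of responders. With small arms the conditional p-value takes few values, so the test cannot use its full nominal level. Boschloo's test takes the Fisher p-value as its statistic but sets the cut-off so that the unconditional size, maximised over the common response rate, stays at or below alpha. Its rejection region contains Fisher's, so it cannot be less powerful.

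This matters most where power is short. Aim 1 in section 12.6 is "To evaluate the efficacy of secukinumab for the complete resolution of mild plaque-type psoriasis after 3 months of secukinumab treatment", and IGA 0 is the co-primary endpoint closest to that wording. It is also the only one with low stated power. The relapse subsets are smaller still. Section 17.1 says that recruitment is closed, so power cannot come from more patients.

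**Working it through.** **Inputs.** From section 12.11: 19 per arm; PASI 75 0.77 v 0.05; PASI 90 0.54 v 0.02; IGA 0 0.24 v 0.01 (first power table); relapse subsets 8:11, 6:13 and 8:6 with their tabled rates. Two-sided 0.05 for relapse is an assumption, because the plan gives 0.05 without sidedness.

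**Method.** Enumerate every outcome (a, b). Power = sum of Bin(a; n1, p1) × Bin(b; n2, p2) over rejected outcomes. Size = the maximum of that sum over p1 = p2. Boschloo's cut-off is the largest Fisher p-value whose rejection region has size at or below alpha.

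**Step 1: the plan's own figures.** One-sided Fisher at 0.001, 0.77 v 0.05, reaches 0.95 power first at 19 per arm (0.964), as stated. One-sided Fisher for IGA 0 at 0.24 v 0.01 gives 0.456 at 0.05 and 0.254 at 0.01, matching 0.46 and 0.25. The row with those powers prints placebo 0.1, which would give 0.173 and 0.060. Two-sided Fisher at 0.24 v 0.01 gives 0.432 and 0.126. So the printed powers come from a one-sided test with placebo 0.01.

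**Step 2: true size at nominal 0.05.** Fisher at 19:19: 0.029 one-sided, 0.028 two-sided. At 8:6: 0.020 two-sided. Boschloo at 19:19 one-sided: 0.049.

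**Step 3: IGA 0 at 19:19, 0.24 v 0.01.**

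| Level | Fisher | Boschloo |
|---|---|---|
| one-sided 0.05 | 0.456 | 0.630 |
| two-sided 0.05 or one-sided 0.025 | 0.432 | 0.456 |
| one-sided 0.01 | 0.254 | 0.254 |

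Almost all of the 17.5-point gain in the first row is one outcome, 4/19 v 0/19. Its one-sided Fisher p is C(19,4)/C(38,4) = 3876/73815 = 0.0525, just above 0.05; its Boschloo p is 0.036. Its probability is [3876 × 0.24^4 × 0.76^15] × 0.99^19 = 0.2096 × 0.8262 = 0.173. In the other rows this outcome is rejected by neither test.

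**Step 4: dependence on final arm sizes** (one-sided 0.05, treated:placebo).
- 19:20: the p-value for 4 v 0 is 3876/82251 = 0.047. Fisher already rejects, and power goes from 0.625 to 0.626.
- 20:19: it is 4845/82251 = 0.059. Only Boschloo rejects, and power goes from 0.480 to 0.671 (19 points).
- 20:20: 0.503 to 0.667.

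Averaged over 20 randomised per arm with independent 5.6% dropout (the plan's rate; independence is an assumption), the mean gain is about 12.5 points one-sided and 0.9 points two-sided (0.496 to 0.505).

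**Step 5: the other co-primaries.** At 19:19 and one-sided 0.05, PASI 75 gains under 0.1 point and PASI 90 about 0.6 point (0.988 to 0.993).

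**Step 6: relapse subsets, two-sided 0.05, at section 12.11's own rates.**

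| Subset | Rates | Fisher | Boschloo |
|---|---|---|---|
| 8:11 | 0.00 v 0.45 | 0.603 | 0.603 |
| 8:11 | 0.13 v 0.73 | 0.673 | 0.749 |
| 8:11 | 0.50 v 1.00 | 0.637 | 0.855 |
| 6:13 | 0.00 v 0.54 | 0.616 | 0.616 |
| 6:13 | 0.17 v 0.77 | 0.667 | 0.751 |
| 6:13 | 0.50 v 1.00 | 0.656 | 0.891 |
| 8:6 | 0.00 v 0.67 | 0.687 | 0.903 |
| 8:6 | 0.13 v 0.83 | 0.680 | 0.702 |
| 8:6 | 0.25 v 1.00 | 0.886 | 0.973 |

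The tabled rows not shown gain 3 to 9 points. Two can be checked by hand:
- **8:6, first row:** the added outcome is 0/8 v 3/6, with Fisher p = C(6,3)/C(14,3) = 20/364 = 0.055. The number relapsing in the group of 6 is Bin(6, 0.67), and P(≥4) = 0.687 becomes P(≥3) = 0.903.
- **6:13, last row:** the added outcome is 4/6 v 13/13, with p = C(6,2)/C(19,2) = 15/171 = 0.088. Power goes from P(X ≤ 3) = 42/64 to P(X ≤ 4) = 57/64 for X ~ Bin(6, 0.5).

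The plan attaches 0.80 power to these rows, which Fisher does not reproduce. They are used here only as rates.

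**The case against.** Fisher's test is valid, pre-specified and the test on which the trial was sized. Preferring Boschloo is a choice about efficiency. That stands.

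The large IGA 0 gain needs one-sided 0.05, which section 12.10 does not state. It falls to 2.4 points at two-sided 0.05 and to nothing at one-sided 0.01, the case behind the plan's own 0.25. It also turns on whether one outcome crosses the threshold, so one patient more or fewer in an arm can remove it. All of this stands, and the claim is limited accordingly.

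Under section 12.7 the primary objective is met once any hypothesis in the order is rejected, so PASI 75 largely decides it, and that barely moves. This also stands: the benefit is to IGA 0 and relapse, not to the headline result.

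Finally, the relapse comparisons are exploratory, and the gain at the first tabled row is nil for 8:11 and 6:13. That is right for those rows, but other rows in the same tables gain 2 to 23 points, and none loses.

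**Conclusion.** The point holds as a cheap improvement. Fisher's test leaves part of the nominal level unused at these sample sizes, and Boschloo's test recovers some of it with no loss of error control. For IGA 0 at 19:19 the gain is 17 points at one-sided 0.05, 2.4 at two-sided 0.05 or one-sided 0.025, and about 0 at one-sided 0.01. For the relapse subsets at the plan's own rates it is 0 to about 23 points at two-sided 0.05.

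Three stronger readings might be inferred, and the documents do not support them:
- **That Fisher's test is a mistake.** Its type I error is controlled, and nothing in the plan contradicts its use.
- **That 17 points are there for the taking.** That figure belongs to one sidedness, alpha and pair of arm sizes, with placebo 0.01. At the printed 0.1, the one-sided 0.05 gain is 6 points (0.173 to 0.235).
- **That the change rescues IGA 0.** At 19 per arm, power is 0.63 at best among the levels shown, still below 0.80.

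The under-1-point gain for PASI 75 and PASI 90 is likewise specific to one-sided 0.05. At two-sided 0.05 PASI 90 gains 1.3 points (0.974 to 0.988). At one-sided 0.001, the sizing level, it gains 11 points with 20 per arm (0.731 to 0.839). Sidedness and alpha must therefore be settled first.

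**What to change.** Before unblinding:
1. State the sidedness and alpha of each comparison of proportions in section 12.10.
2. Name Boschloo's exact test for the primary and relapse proportions, with Fisher's test as a sensitivity analysis.
3. Restate power in section 12.11 at that alpha, and reconcile the two IGA 0 placebo rates (0.01 and 0.1).
4. Use a 95% confidence interval method consistent with the chosen test, so that interval and p-value do not disagree.

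If the data are already unblinded, keep Fisher as primary and report Boschloo as supportive only, because a change of test would then be open to the charge of being chosen on the result.

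The cost is a short amendment and a rewrite of the Fisher-based power text; the test is in standard software and needs no patients. The downside is that the gain may be small or nil at the alpha and arm sizes finally reached.

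### The odds ratio is the only between-group measure named for proportions; on the plan's placebo rates it would often be infinite, and no zero-cell rule or interval method is given

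*Combined protocol and SAP*

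**What the plan says.** Section 12.10 sets one rule for all comparisons of proportions: "For the comparison between proportions a Fisher exact test will be performed in any case". On reporting, it plans contingency tables and says that "odd ratios will be calculated". It then adds "95% Confidence Intervals will be provided", without saying for which quantity or by which method. It names no risk difference or risk ratio and says nothing about a table with an empty cell.

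Section 12.11 gives the rates behind the design, taken from two published phase 3 trials in moderate or severe disease, with 19 evaluable patients per group (20 recruited):

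- PASI 75: "largest Placebo proportion=0.05 and smallest Secukinumab proportion=0.77".
- PASI 90 (treatment, placebo, difference): "PASI 90 0.54 0.02 0.52".
- IGA 0, first power table: "IGA0 0.24 0.01 0.23".
- IGA 0, second power table: "IGA 0 0.24 0.1 0.14".

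The two IGA 0 rows disagree on the placebo rate, 0.01 against 0.1.

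**The concern.** With placebo response this rare and only 19 patients in the arm, a placebo group with no responders is an ordinary outcome. The sample odds ratio then divides by zero, and its interval has no upper limit. A trial that follows section 12.10 as written would often report a p-value for its co-primary endpoints with no finite estimate of the treatment effect.

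The problem is largest for IGA 0, the clearance endpoint. That is the endpoint closest to Aim 1 (complete resolution), and its stated power is only 0.46 at the 0.05 level, so the interval would have to carry much of the information. With no rule fixed in advance, the remedy (adding 0.5, a penalised estimate, another measure) would be chosen after the table has been seen.

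**Working it through.** **Reproducing the plan's figures.** Two binomials were enumerated exactly with a one-sided Fisher test.

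- Sample size for PASI 75 (0.77 against 0.05, significance level read as 0.001, power 0.95): power is 0.943 at 18 per group and 0.964 at 19. The stated 19 is reproduced.
- Power at 19:19, at the 0.05 and 0.01 levels:

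| Endpoint | Placebo rate used | Stated | Recomputed |
|---|---|---|---|
| PASI 75 | 0.05 | 0.99 / 0.99 | 1.00 / 0.996 |
| PASI 90 | 0.02 | 0.99 / 0.94 | 0.988 / 0.943 |
| IGA 0 | 0.01 | 0.46 / 0.25 | 0.456 / 0.254 |
| IGA 0 | 0.1 | 0.46 / 0.25 | 0.173 / 0.060 |

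The stated IGA 0 power was therefore computed with 0.01. The 0.1 in the second table, and the difference of 0.14 beside it, look like a misprint.

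**Chance that the odds ratio is not finite.** Let a and b be treated responders and non-responders, and c and d the same for placebo. The sample odds ratio ad/(bc) has a zero denominator when no placebo patient responds or every treated patient responds. With n per group:

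P = 1 − [1 − (1 − p_placebo)^n] × [1 − p_treated^n]

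At n = 19:

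- PASI 75: 0.95^19 = 0.377 and 0.77^19 = 0.007, so P = 1 − 0.623 × 0.993 = 0.382.
- PASI 90: 0.98^19 = 0.681; the treated term is negligible, so P = 0.681.
- IGA 0 (0.01): 0.99^19 = 0.826, so P = 0.826.
- IGA 0 (0.1, if the second table were right): 0.90^19 = 0.135, so P = 0.135.

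With all 20 recruited per group analysed, the four figures are 0.362, 0.668, 0.818 and 0.122.

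Nearly all of these cases are infinite. A true 0/0 needs no responder in either arm; for IGA 0 that is 0.99^19 × 0.76^19 = 0.826 × 0.0054 = 0.004.

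**What would be reported.** The illustrative tables below have 19 per group. The 15, 10 and 5 treated responders are near the expected 0.77 × 19 = 14.6, 0.54 × 19 = 10.3 and 0.24 × 19 = 4.6.

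| Treated vs placebo responders | Conditional odds ratio, exact 95% CI | Risk difference, Newcombe 95% CI |
|---|---|---|
| 15 vs 0 | infinite (10.2 to infinity) | 0.79 (0.51 to 0.91) |
| 10 vs 0 | infinite (3.5 to infinity) | 0.53 (0.26 to 0.73) |
| 5 vs 0 | infinite (1.03 to infinity) | 0.26 (0.04 to 0.49) |
| 15 vs 1 | 57 (6.0 to 2,991) | 0.74 (0.44 to 0.87) |

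The last row shows that one placebo responder makes the odds ratio finite but still very imprecise.

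**Relapse proportions.** The same sentence of section 12.10 governs these comparisons. Section 12.11 expects subgroups of 8:11, 6:13 and 8:6. Of the 12 detectable scenarios it lists (5 + 4 + 3), 6 contain a relapse proportion of 0.00 or 1.00 (2 in each table), where the odds ratio is zero or infinite. No probability is attached to these, because the plan assumes no relapse rate.

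**The case against.** Several points on the other side have force.

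- **The result would not be empty.** A reader might infer that the trial would yield no usable effect size or interval. The documents do not support that. The planned contingency tables show each arm's count and proportion, so a reader can form the difference. An exact interval also keeps an informative lower limit, such as 10.2 for 15/19 against 0/19. What is lost is a finite between-group estimate and an upper limit.
- **Powering on a difference and reporting an odds ratio is not a contradiction.** The power tables express the alternative as a difference in proportions. An odds ratio of 1 and a difference of 0 are the same null hypothesis, so the change of scale is not an error in itself. The case for the risk difference is that it stays estimable.
- **The percentages depend on the placebo rates and the estimator.** Section 15.2 mentions a placebo response of 5 to 10% without tying it to an endpoint. If 10% applied to PASI 75, the figure would be 1 − (1 − 0.135) × (1 − 0.007) = 0.141, about 14% instead of 38%. The rates also come from more severe disease. A continuity-corrected or penalised odds ratio would be finite and is compatible with the text, but the plan chooses none.
- **Section 12.10 may be incomplete.** One sentence about the primary objective breaks off, and the intervals could be meant for the separate proportions. So the safe statement is that the odds ratio is the only between-group measure named for proportions.
- **The trial is described as exploratory, and its tests are unaffected.** This is true, and it limits the point to estimation and reporting.

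**Conclusion.** The point holds as one about estimation. On the rates that reproduce the plan's own power, at 19 per group, the only between-group measure named for proportions would have no finite value in about 38% of trials for PASI 75, 68% for PASI 90 and 83% for IGA 0. With 20 per group the figures are 36%, 67% and 82%.

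These figures assume the uncorrected sample odds ratio and placebo rates of 0.05, 0.02 and 0.01. The IGA 0 figure falls to about 14% if the 0.1 in the second table were correct, but the power stated in that table rules this out as the value used. The Fisher tests, the testing order and the sample size are not in question. The change is worth making because a measure that stays finite can be computed from data already planned.

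**What to change.** In section 12.10:

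- Make the risk difference with a score-type 95% confidence interval (Miettinen-Nurminen or Newcombe, one named in advance) the effect measure for PASI 75, PASI 90 and IGA 0.
- Use the same measure for the relapse proportions, where the small subgroups make empty cells possible.
- Report the odds ratio as supplementary, with an exact conditional 95% interval, shown as infinite where it is.

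In section 12.11, correct the IGA 0 row of the second power table so that its placebo rate and difference agree with the first table (0.01 and 0.23). The stated power then stands.

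The cost is a sentence or two in section 12.10 and one corrected table row. No new data are needed, and the Fisher test and the sample size do not change.

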- 4) Elapsed time from week 24 until relapse occurs before week 72, measured in weeks.
- 5) The proportion of subjects who achieve a PASI 100 or PASI 90 response at week 12
- 6) Frequency and severity of all AEs and SAEs that occur during the whole trial including the observational period (AEs and SAEs include but not limited to comorbidities, such as hypertension, diabetes, and cardiovascular diseases).

12.9 * Methods and Procedures

Please provide a description of the laboratory and clinical analyses and procedures that will be performed. Include the role of external collaborators and consultants when appropriate. Please refer to Help text for Guidance.

The trial will be conducted as a unicenter, randomized, double-blind, parallel-group, placebo-controlled exploratory study of Secukinumab in subjects with mild plaque-type psoriasis. The purpose of the study is to evaluate the efficacy and the safety of Secukinumab for 3 or 6 month treatment periods, and to explore whether relapse occurs after the medication has been discontinued, during the subsequent 12 month observation period.

Arms: (Group 1: 6 months of Secukinumab) vs. (Group 2: 3 months of Secukinumab). Patients will be randomly assigned in a 1:1 ratio to Group 1 or Group 2. Group 1 receives Secukinumab at a dose of 300 mg with injections administered once weekly at baseline and at weeks 1, 2, 3, and 4 and then every 4 weeks for 6 months of period until week 12.

Patients randomly assigned to Group 2 will receive placebo injections corresponding to the Group 1 regimen until week 8 in order to maintain a double-dummy design until week 12. However, Group 2 will receive Secukinumab at a dose of 300 mg with injections administered **once weekly at week 12 and at weeks 13, 14, 15, and 16 and then every 4 weeks for 3 months** of period. Both group 1 and 2 discontinue Secukinumab after week 24 being observed from week 25 to week 72 (48 weeks).

Both Group 1 and Group 2 patients will not receive topicals or any other therapies except Secukinumab during the study periods, including placebo and observation periods.

Secukinumab is dosed weekly for the first 4 weeks (ramp up) the monthly (maintenance). In order to maintain the blind for the 2 dose groups, group 1 will resume weekly injection weeks 12 through 16. The injections given at weeks 13, 14, and 15 will be placebo.

Visit	Group 1		Group 2		Skin biopsy & blood
1	Screening	Screening			

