- Physical exam (symptom driven as indicated)
- Vital signs (blood pressure, temperature and pulse).
- POCT Pregnancy
- Assessment of psoriasis, PGA, PASI with BSA, PASE, DLQI
- Adverse event assessment
- Dose of Secukinumab 300 mg or placebo by subcutaneous injections

Visit 8 and 14 --(Week 12 and 24)

- Physical exam (symptom driven as indicated)
- Vital signs (blood pressure, temperature and pulse).
- POCT Pregnancy
- Fasting Blood: Comprehensive metabolic profile, CBC, lipids and HgB A1c.
- Research blood
- Two 6mm skin biopsies, 1 lesional, 1 non-lesional. The lesional sample will be taken from the area the lesions were before.
- Medical photography
- Assessment of psoriasis, PGA, PASI with BSA, PASE, DLQI
- Adverse event assessment
- Dose of Secukinumab 300 mg or placebo by subcutaneous injection
- Observation period of 15 minutes (+/- 5 minutes) post study drug administration week 12 only
- Subject will be offered a meal at end of visit

Visit 15,16, and 17 —(Week 36, 48 and 60) Observation

- Physical exam (symptom driven as indicated)
- Vital signs (blood pressure, temperature and pulse)
- POCT Pregnancy
- Assessment of psoriasis, PGA, PASI, with BSA, PASE, DLQI
- Adverse event assessment

Visit 18 --(Week 72)

- Physical exam (symptom driven as indicated)
- Vital signs (blood pressure, temperature and pulse)
- POCT Pregnancy

- Fasting Blood: Comprehensive metabolic profile, CBC, lipids and Hgb A1c
- Research Blood
- Skin biopsy is optional when recurrence occurs after Week 24. Two 6mm skin biopsies, 1 lesional, 1 non-lesional. The lesional sample will be taken from the area the lesions were before.
- Medical photography
- Assessment of psoriasis, PGA, PASI with BSA, PASE, DLQI
- Adverse event assessment
- Observation period
- Subject will be offered a meal at end of visit.

*Visit window will be +/- 1 day for weekly visits (weeks 1, 2, 3, 4, 13, 14, 15,16) and +/- 2 days for all other visits (weeks 8, 12, 20, 24, 36, 48, 60, 72).

Unscheduled Visit--(as necessary)

Subjects will return to RUH for evaluation and/or additional blood work, as per the PI's discretion.

Relapse Visit

- Research Blood
- Skin biopsy is optional. Two 6mm skin biopsies, 1 lesional, 1 non-lesional.
- Medical photography
- Assessment of psoriasis, PGA, PASI with BSA, PASE, DLQI
- Adverse event assessment

Early Termination visit

- Research Blood
- Skin biopsy is optional. Two 6mm skin biopsies, 1 lesional, 1 non-lesional.
- Medical photography

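### Time to relapse has a value only for patients who relapse, yet a Wilcoxon test is mandatory and sized on all 38; no rule says how relapse-free patients and early leavers enter it or whether it or the log-rank test decides

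*Combined protocol and SAP*

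**What the plan says.** Section 12.8, item 4, defines the outcome as "Elapsed time from week 24 until relapse occurs before week 72, measured in weeks". Section 12.10 prescribes the test: "The comparison between times of relapse must be done using a Wilcoxon-Mann-Whitney test". It then adds a second analysis of the same outcome: "A Kaplan Meier analysis will be used to establish the relapse survival curve for each group and" "the log-rank test will be made". The only testing order in 12.10 concerns the three week 12 endpoints (PASI 75, PASI 90, IGA 0).

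Section 12.11, item 3, is headed "Power Analysis for Exploratory Objective/Second outcome". It reads "To compare the time to relapse between groups with a sample size of 19:19 a Wilcoxon-Mann-Whitney test for nonrelated samples" and, at power 0.8, "will be able to detect differences only if the effect size observed is equal or larger than 0.96". It names no effect-size scale and gives no figure for the log-rank test.

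The documents foresee both kinds of patient for whom a rule is needed. Preventing relapse is aim 2 in 12.6, so relapse-free patients are the hoped-for result. Section 12.11 assumes 5.6% dropout, and 12.9 lists an "Early Termination visit" at which PASI is recorded.

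**The concern.** A patient who reaches week 72 without relapse has no value on the outcome as defined. If the mandatory test is run on that outcome, those patients drop out of it. What remains is a comparison within relapsers, a subset selected by a post-randomisation event, so it no longer has the protection of randomisation. It also ignores the main way in which treatment could help, by leaving fewer patients to relapse.

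The power statement works on a different footing: 19:19 means that all evaluable patients are ranked. Nothing joins the two. The plan does not say whether relapse-free patients are excluded, ranked last or censored, or what happens to early leavers. The log-rank test can keep all of them, but no censoring time is written, and the plan does not say which result stands if the two tests disagree. As written, these choices could be made after the relapse data are seen, on the outcome that speaks most directly to aim 2.

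**Working it through.** **1. Reproducing the 0.96.** Inputs from 12.11 item 3: 19 per group, power 0.80, significance level 0.05. Assumed: two-sided test, standardised mean difference, normal parent.
- Wilcoxon efficiency against the t-test is 3/π = 0.955, so the effective n is 19 × 0.955 = 18.14 per group, with 2 × 18.14 − 2 = 34.3 degrees of freedom and a critical t of 2.032.
- Noncentrality at 0.96: 0.96 × √(18.14/2) = 2.89. Power is 0.802.
- Solving for power 0.80 gives 0.957. A one-sided test would give 0.84.

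The figure is therefore correct for 38 patients who all have an observed time.

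**2. What the missing rule does to power at 0.96.** The documents forecast no relapse rate, so the shares below are assumptions. Simulation: normal shift of 0.96 SD, 19:19, one common cutoff set so that the stated share of all patients relapses, tie-corrected Wilcoxon, two-sided 0.05, 6000 replicates.

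| Share relapsing (assumed) | Relapsers only | Relapse-free ranked last |
|---|---|---|
| 100% | 0.80 | 0.80 |
| 90% | 0.63 | 0.79 |
| 75% | 0.41 | 0.79 |
| 50% | 0.16 | 0.73 |

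A continuity correction lowers these by about 0.01 to 0.02.

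**3. The two tests side by side.** Assumed 48-week relapse rates, constant hazards, relapse dated at the 12-week visits, nobody leaving early. Power in %:

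| Relapse rates | Wilcoxon, relapsers only | Wilcoxon, ranked last | Log-rank |
|---|---|---|---|
| 50% vs 90% | 18 | 82 | 86 |
| 50% vs 80% | 9 | 50 | 54 |
| 50% vs 50% | 5 | 5 | 5 |

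This ordering depends on the hazard shape. With an assumed early difference that fades (relapse risks over successive 12-week intervals of 20/30/40/50% against 60/40/40/40%), power is about 0.69 in relapsers only, 0.68 ranked last and 0.50 for log-rank.

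**4. Early leavers.** An assumed extreme case: 60% relapse in both groups, dropout 0% against 40%. Treating a leaver's last time as a relapse time gives false-positive rates of 0.18 to 0.32; ranking leavers last gives 0.07 to 0.09; log-rank with censoring stays at 0.04 to 0.05. The plan's own 5.6% is about one patient per group (0.056 × 20 = 1.1), so the effect at that level would be far smaller.

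**5. The missing log-rank figure.** Schoenfeld at 80% power, two-sided 0.05: HR = exp(−(1.960 + 0.842) × 2/√events). This gives 0.40 with 38 relapses, 0.33 with 26 and 0.28 with 19. It is a large-sample formula. Simulation at 19:19 under proportional hazards gives about 76% power at 0.40 with 38 relapses and 77% at 0.28 with 19. About 80% is reached at 0.38 with 38, 0.33 with 26 and 0.26 with 19.

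**The case against.** The strongest reply is that relapsers-only is just one reading, and that the plan points away from it. The power statement counts 19:19, and the Kaplan-Meier and log-rank analysis keeps relapse-free patients. Read that way, power at 0.96 stays between 0.73 and 0.80. This stands: a reader might infer that the plan commits itself to comparing relapsers only, and the documents do not show that. They leave it open, with a definition that points one way and a sample size that points the other.

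A second reply is that the Wilcoxon test carries a must and the only power figure, so it leads and log-rank supports. That is plausible, but the plan does not say so, and a leading test still needs a rule for patients without a value.

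A third is that preferring log-rank is partly a matter of taste. This stands in part. With complete follow-up and relapse-free patients ranked last, the Wilcoxon test is sound. It is only 4 points behind log-rank in the two constant-hazard scenarios with a difference shown, and ahead when the difference is early and fades. The case for log-rank is that it is already planned and handles early leavers under one stated rule, not that it always has more power.

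Finally, the outcome is secondary, labelled exploratory, and accompanied by a Fisher test on relapse proportion. That limits the stakes but does not supply the rule.

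**Conclusion.** The point holds as a gap that should be closed. The time is defined for relapsers only, the mandatory test is sized as if all 38 had one, and neither the handling of the others nor the deciding test is stated. How much this matters depends on the relapse rate, which the documents do not give: the choice of rule moves power at 0.96 from about 0.79 to 0.63 if 90% relapse, and from about 0.73 to 0.16 if half do. These figures rest on a standardised mean difference scale, a normal shift and no early withdrawal.

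Three stronger conclusions are not supported. The 0.96 is not an arithmetic error; it reproduces, and its weakness is the unstated condition behind it. The Wilcoxon test is not invalid in itself. And nothing here touches the week 12 analysis or the Fisher comparison of relapse proportions.

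**What to change.** Make the change before outcome data are examined. Section 17.1 says recruitment is closed, while 14.1 still projects 50 outpatient visits in the coming year.

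1. **Section 12.10, deciding test.** State that time to relapse is compared in all patients who enter observation and for whom relapse is defined, that is, with some PASI improvement at week 24. Make the already planned log-rank test decisive, with relapse-free patients and early leavers censored at their last PASI assessment.
2. **Section 12.10, supportive test.** Keep the Wilcoxon test, never restricted to relapsers. Rank patients relapse-free at week 72 last, and use the censored (Gehan) form if anyone leaves early. Add a sensitivity analysis that counts leaving because of worsening psoriasis as a relapse.
3. **Section 12.11, item 3.** Name the effect-size scale. State that 0.96 requires all 38 patients to be ranked with few relapse-free, and that power falls to about 0.73 if half do not relapse. Add the log-rank hazard ratio detectable at about 80% power, by simulation under proportional hazards: about 0.38 with 38 relapses, 0.33 with 26 and 0.26 with 19.

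The cost is a few sentences and one short sensitivity analysis. No new visits or patients are needed, and PASI is already scheduled at week 72 and at early termination; the reason for leaving must be on record. The downsides: the stated sensitivity becomes less favourable and depends on an assumed number of relapses, and log-rank can lose power to the ranked-last Wilcoxon test if the difference is early and fades.
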